1.6 MODIFICATIONS FROM THE APPROVED STATISTICAL ANALYSIS PLAN

Not applicable.

2 COLLECTED DATA

Data collected on AD patients and healthy volunteers at screening and baseline are:

- Informed consent/assent form.
- Inclusion and exclusion criteria.
- Demographic data (age, sex, race and ethnicity).
- Medical/surgical history.
- Prior medications/procedures.
- Physical measurements (height and body weight).
- Urine pregnancy test for females with childbearing potential only.
- AD disease characteristics are assessed by clinical-reported outcome assessments (ClinROs) (EASI and ISS) and PROs via eDiary (POEM, CDLQI and Worst itch/Sleep disturbance/Skin pain NRS).
- Skin barrier function and structure evaluated by TEWL, STS, OCT, FTIR, and 2D and 3D photographs.
- Safety will be assessed by adverse events, vital signs (including heart rate, systolic and diastolic blood pressure, pulse rate, body temperature, and respiratory rate), physical examination.
- For AD patients only: attribution of the dose regimen for study treatment administration according to approved label.
- Standardized photographs of (predefined lesional/non-lesional or healthy) skin area used for TEWL and standardized full body photographs.

Data collected on AD patients and healthy volunteers after baseline (treatment phase (if applicable) and follow-up) are:

- Urine pregnancy test for females with childbearing potential only.
- Concomitant medications/procedures.
- Safety will be assessed by adverse events, vital signs (including heart rate, systolic and diastolic blood pressure, pulse rate, body temperature, and respiratory rate) and physical examination.
- AD disease characteristics are assessed by ClinROs (EASI and ISS) and PROs via eDiary (POEM, CDLQI and Worst itch/Sleep disturbance/Skin pain NRS).
- Skin barrier function and structure evaluated by TEWL, STS, OCT, FTIR, and 2D and 3D photographs.
- For AD patients only: study treatment administration according to approved label.
- Standardized photographs of (predefined lesional/non-lesional or healthy) skin area used for TEWL and standardized full body photographs.

3 GENERAL STATISTICAL APPROACH

Two final analyses will be performed:

- One for the treatment phase: based on all patients and performed on data collected until the EoT visit (Week 16). This will be done once the last evaluable participant has completed his/her EoT visit.
- One for the follow-up period: based on all participants and all data.

The quantitative variables will be summarized using the following parameters:

- Number of non-missing data.
- Mean.
- Standard deviation (SD).
- Standard Error of the Mean (SEM).
- Median.
- Minimum.
- Maximum.

The qualitative variables will be summarized using the following parameters:

- Number of non-missing data,
- Counts and percentages.

Missing data or unknown responses will not be counted in the percentages.

The following definitions will be used in this document:

- Cohort: the study includes 2 cohorts: patients with moderate-to-severe AD cohort and a healthy volunteers cohort.
- Group: 3 groups are identified: patients' lesional skin area group, patients' non-lesional-skin area group, and healthy volunteers' normal skin group.

4 ANALYSIS OF PATIENT DATA

4.1 ANALYSIS VARIABLES

4.1.1 Baseline variables

Baseline characteristics (demographics, medical history, prior medications, vital signs, physical examination and disease characteristics) are collected.

No electrocardiogram and clinical safety laboratory assessments are required in this study.

4.1.2 Main evaluation variable(s)

The primary endpoint is the percent change from baseline in TEWL after 5 STS assessed on lesional skin at Week 16 in AD patients.

4.1.3 Secondary evaluation variable(s)

The secondary endpoints are:

- Change (percent and absolute) from baseline in TEWL after 5, 10, 15, 20 STS assessed on lesional skin at Week 16 in AD patients.
- Change (percent and absolute) from baseline in TEWL after 5, 10, 15, 20 STS assessed on non-lesional skin at Week 16 in AD patients.
- Change (percent and absolute) from baseline in TEWL after 5, 10, 15, 20 STS assessed on normal skin at Week 16 in healthy volunteers.
- Change (percent and absolute) from baseline in TEWL before STS on lesional skin in AD patients over time.
- Change (percent and absolute) from baseline in TEWL before STS on non-lesional skin in AD patients over time.
- Change (percent and absolute) from baseline in TEWL before STS on normal skin in healthy volunteers over time.
- Change (percent and absolute) from baseline in TEWL area under the curve (TEWL AUC: a composite measure before and after 5, 10, 15, and 20 STS) for skin barrier function in lesional skin in AD patients over time.
- Change (percent and absolute) from baseline in TEWL AUC (a composite measure before and after 5, 10, 15, and 20 STS) for skin barrier function in non-lesional skin in AD patients over time.
- Change (percent and absolute) from baseline in TEWL AUC (a composite measure before and after 5, 10, 15, and 20 STS) for skin barrier function in normal skin in healthy volunteers over time.

- Change (percent and absolute) from baseline in TEWL after STS assessed on lesional skin in AD patients over time.
- Change (percent and absolute) from baseline in TEWL after STS assessed on non-lesional skin in AD patients over time.
- Change (percent and absolute) from baseline in TEWL after STS assessed on normal skin in healthy volunteers over time.

4.1.4 Tertiary/exploratory evaluation variable(s)

The tertiary/exploratory endpoints are:

- Change (percent and absolute) from baseline in epidermal hypertrophy parameters including epidermal thickness, superficial plexus depth, blood vessel diameter and density measured by OCT over time.
- Change (percent and absolute) from baseline in stratum corneum lipid structure measured by FTIR spectroscopy in conjunction with tape-stripping over time.
- Change (percent and absolute) from baseline in EASI (total score) over time.
 - The EASI is a composite index with scores ranging from 0 to 72. Four AD disease characteristics (erythema, thickness [induration, papulation, and edema], scratching [excoriation], and lichenification) will be assessed for severity by the Investigator or designee on a intensity scale of “0” (absent) through “3” (severe). In addition, the area of AD involvement will be assessed as a percentage by body area of head and neck, trunk, upper limbs, and lower limbs, and converted to a area score of 0 to 6. In each body region, the area score is expressed as 0, 1 (1% to 9%), 2 (10% to 29%), 3 (30% to 49%), 4 (50% to 69%), 5 (70% to 89%), or 6 (90% to 100%).
 - Even if the EASI scores are available in the SDTM database, the intermediate and total EASI scores will be derived as follows. However, only the total EASI score will be analyzed.
 - Severity scores: for each region (Head and neck, Trunk, Upper limbs and Lower limbs), the severity score will be derived as follows, ranging from 0 to 12:
$$\text{Severity score}_R = \text{Intensity score}_{\text{Erythema}, R} + \text{Intensity score}_{\text{Edema/Papulation}, R} + \text{Intensity score}_{\text{Excoriation}, R} + \text{Intensity score}_{\text{Lichenification}, R},$$
where R = region.
 - Region scores: for each region, the region score will be derived as follows:
$$\text{Region score}_R = \text{Severity score}_R * \text{Area score}_R * \text{Multiplier}$$
where R = region, Multiplier = 0.1 (or 0.2 for children <8 years) for Head and Neck region, 0.3 for Trunk, 0.2 for Upper Limbs, 0.4 (or 0.3 for children <8 years) with the age calculated at each visit.
 - Total EASI score will be derived as the sum of the 4 region scores, ranging from 0 to 72.

- Change (percent and absolute) from baseline in ISS (total score) over time:
 - Total ISS score will be derived as the sum of the four target lesions (Erythema, Infiltration/Papulation, Excoriations and Lichenification), ranging from 0 to 12.
- Change (percent and absolute) from baseline in POEM (total score) over time.
- Change (percent and absolute) from baseline in CDLQI (total score) over time.
- Change (percent and absolute) from baseline in assessment of worst itch NRS (scale) over time.
- Change (percent and absolute) from baseline in sleep disturbance NRS (scale) over time.
- Change (percent and absolute) from baseline in skin pain NRS (scale) over time.
- Change (percent and absolute) from baseline in photograph outputs (TiVi and skin roughness indexes) obtained from skin imaging over time.
- Correlation between baseline values of TEWL before and after STS, and TEWL AUC in lesional and non-lesional skin of AD patients with the following baseline measures:
 - EASI.
 - Targeted lesion ISS.
 - Image-derived severity score in targeted lesional skin.
 - Quantified epidermal hypertrophy and structure changes in OCT and FTIR.
- Correlation between percent change from baseline in TEWL before and after STS, and TEWL AUC in lesional and non-lesional skin of AD patients at Week 8, Week 16 and Week 28 with corresponding change from baseline in the following measures:
 - EASI.
 - Targeted lesion ISS.
 - Image-derived severity score in targeted lesional skin.
 - Quantified epidermal hypertrophy and structure changes in OCT and FTIR.

4.2 ANALYSIS POPULATIONS

The following analysis populations will be defined:

4.2.1 Enrolled population

The enrolled population will be defined by all participants who sign the informed consent form.

4.2.2 Intent-to-treat population

The intent-to-treat (ITT) population will include all enrolled patients, who received at least 1 dose of investigational medicinal product (IMP) and all enrolled healthy volunteers who have at least 1 TEWL/STS assessment performed, irrespective of compliance with the study protocol and procedures.

The ITT population will be used for efficacy analyses.

4.2.3 Modified Intent-to-treat population

The modified intent-to-treat population (mITT) will include all ITT participants. If prohibited therapies for atopic dermatitis (AD) are used and assessed by the study team as having a significant impact on skin barrier only visits prior to rescue treatment use are considered.

The mITT population will be used for efficacy analyses.

4.2.4 Safety population

The safety population will include all patients, who actually received at least 1 dose of IMP or had at least 1 TEWL/STS assessment and all healthy volunteers who have at least 1 TEWL/STS assessment performed.

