4.3.5 Analyses of safety parameters

All the safety analyses will be performed using the safety population. When applicable, results will be by cohort and overall.

The safety analysis will be conducted according to the Sponsor's document "Analysis and reporting of safety data from Clinical Trials through the Clinical Study Report" (BTD-009536 Version 3.0 dated on 24 May 2014).

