4.3.5.1 Adverse events

Adverse events will be coded to a lower level term (LLT), PT, HLT, high level group term (HLGT) and primary SOC using the version of MedDRA in effect at Sanofi at the time of each database lock.

For patients' cohort, they will be classified into predefined standard categories according to chronological criteria:

- Pre-treatment AEs: AEs that occurred, worsened or became serious during the pre-treatment period defined as the time between informed consent signature and the first IMP administration.
- Treatment emergent AEs (TEAEs): AEs that occurred, worsened or became serious during the TEAE period defined as the time from the first IMP administration up to the EoT visit (EoT included).
- Post-TEAEs: AEs that occurred, worsened or became serious during the post-TEAE period defined as the time starting after the TEAE period (including the follow-up period).

Treatment-emergent AEs will be assigned to the treatment received at the time of the AE onset. If the onset date (or time) of an AE (occurrence, worsening or becoming serious) is incomplete or missing, then the AE will be considered as a TEAE unless a partial date (or time) shows it as a pre- or post-treatment event.

For all healthy volunteers, safety data will be considered as part of a single period starting with the signature of the informed consent and ending with the EoS visit (EoS included).

All AEs reported in the study will be listed, sorted by participant, onset date and time.

The following TEAEs summaries will be provided for the patients' cohort of the safety population:

- Overview of TEAEs: number and percentage of participants with any TEAE, any serious TEAE, any TEAE leading to death (if any occurred), any TEAE leading to permanent treatment discontinuation, and any TEAE of special interest.
- Summary of TEAEs by primary SOC and PT:
 - Number and percentage of patients with at least one TEAE.
 - Number of occurrences of TEAEs.

Patients presenting TEAEs will be listed sorted by primary SOC and PT. By definition, no TEAEs summary will be displayed for healthy volunteers. AEs that occur outside the treatment-emergent period or in healthy volunteers will be summarized separately.

In addition, the following listings/summary will be provided:

- Listing of any deaths and serious AEs.
- Listing of any AEs leading to permanent treatment discontinuation.

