- c Dose regimen 1: Children with baseline $15 \text{ kg} \leq \text{body weight} < 30 \text{ kg}$ will receive a SC loading dose of dupilumab 600 mg (2 injections of dupilumab 300 mg) on Day 1 (V02), followed by every 4-week SC dosing of dupilumab 300 mg until Week 12 (at Week 0 [(Day 1], Weeks 4, 8, and 12).
- Dose regimen 2: Children with baseline $30 \text{ kg} \leq \text{body weight} < 60 \text{ kg}$ will receive a SC loading dose of dupilumab 400 mg (2 injections of dupilumab 200 mg) on Day 1 (V02), followed by bi-weekly SC dosing of dupilumab 200 mg until Week 14 (at Week 0 (Day 1), Weeks 2, 4, 6, 8, 10, 12, and 14).
- d Assessments on treatment days have to be conducted before administration of dupilumab.
- e Predefined lesional and non-lesional skin areas. TEWL will be measured at each of the 3 closely adjacent spots within the predefined skin areas at all visits without STS and before STS at visits with STS.
- f TEWL will be conducted before STS and then after 5, 10, 15, and 20 STS in lesional skin and non-lesional skin.
- g At Weeks 0, 8, 16, and 28, STS will be conducted on the first spot within the predefined skin area. At Week 2 STS will be conducted on the second spot within the predefined skin area. At Weeks 4, 12, and 22 STS will be conducted on the third spot within the predefined skin area. TEWL will be assessed in lesional skin and non-lesional skin before STS and after 5, 10, 15, and 20 STS. All skin tape strips should be collected and stored.
- h In case STS assessment is to be conducted at an unscheduled visit or at a premature EoT visit the assessment should be conducted at that spot of the skin area, for which the period passed since the last STS assessment is the longest.
- i OCT will be done before STS/TWL, and FTIR will be done before and during STS.
- j Worst itch NRS, Sleep disturbance NRS and Skin pain NRS will be assessed daily from Day -7 to Day -1; daily from Day 1 to Week 4 and then 7 days prior to Week 6, Week 8, Week 12, Week 16, Week 22, and to Week 28 by e-diary.
- k eDiary will be dispensed to the patients at screening (Visit 01) and will be collected on Week 28 (Visit 14). The PROs will be administered to patients via eDiary. Patients will bring the eDiary to the site at each visit, and it will be reviewed for any questionnaires omission and dispensed back to patients at each visit.

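### TEAE, AESI, exposure and compliance tables use a safety population that can include AD patients who were never dosed

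*SAP*

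**What the plan says.** Section 4.2.4 gives AD patients two alternative routes into the safety population: they "received at least 1 dose of IMP or had at least 1 TEWL/STS assessment". Healthy volunteers enter on a TEWL/STS assessment. The ITT definition in 4.2.2 is stricter for AD patients and takes "all enrolled patients, who received at least 1 dose of investigational medicinal product (IMP".

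Section 4.3.5 states: "All the safety analyses will be performed using the safety population". Section 4.3.5.1 repeats this for the treatment-emergent tables: "The following TEAEs summaries will be provided for the patients' cohort of the safety population". The treatment-emergent period is "the time from the first IMP administration up to the EoT visit (EoT included". When the onset of an event is missing or incomplete, "then the AE will be considered as a TEAE unless a partial date (or time) shows it as a pre- or post-treatment event".

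Section 4.3.2.4 also summarises exposure and compliance for the AD cohort of the safety population. Duration of exposure is computed from the first and last dose dates. Compliance is a ratio whose denominator counts the administrations planned up to the last IMP administration.

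The schedule in Appendix B (8.2) puts the first TEWL/STS assessment and the first injection at the same visit, Day 1. Its footnote d, attached to the skin barrier tests, fixes the order: "Assessments on treatment days have to be conducted before administration of dupilumab".

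**The concern.** The population and the quantities summarised in it start from different events. A child enters the safety population at the first TEWL/STS assessment, while the treatment-emergent period, exposure and compliance begin at the first injection. Because the assessment comes first, a child can have the tape stripping on Day 1 and then not be injected. That child is counted in N for the TEAE and AESI tables but has no period in which a dated event could count.

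What is at stake is the description of adverse event incidence on dupilumab in a cohort of about 24 children, where one patient is about 4 percentage points of the denominator (1/24 = 4.2%). There are also two secondary effects. Exposure and compliance have no value for such a child, so N in those tables would depend on a programming choice. And the default for missing onset dates carries no condition that the patient was dosed.

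**Working it through.** **Inputs**

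- Planned AD enrolment: approximately 24, to give 20 evaluable patients with 15% drop-out (SAP 1.3).
- k, the number of AD patients assessed on Day 1 but never dosed: not given in the SAP. The range 0 to 2 is assumed as plausible; 3 and 4 are shown to display the trend.
- x, the number of dosed patients with a TEAE: illustrative.
- The AD part of the safety population is taken as 24, including the k undosed patients.

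**Reproducing the planned number**

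20/(1 - 0.15) = 23.53, rounded up to 24. This agrees with the SAP.

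**TEAE percentage**

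As written: x/24. On dosed patients only: x/(24 - k). The ratio of the first to the second is (24 - k)/24, whatever x is.

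| k | Dosed patients | Factor (24 - k)/24 | x = 10, as written | x = 10, dosed only |
|---|---|---|---|---|
| 0 | 24 | 1.000 | 41.7% | 41.7% |
| 1 | 23 | 0.958 | 41.7% | 43.5% |
| 2 | 22 | 0.917 | 41.7% | 45.5% |
| 3 | 21 | 0.875 | 41.7% | 47.6% |
| 4 | 20 | 0.833 | 41.7% | 50.0% |

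With x = 12 and k = 1, 12/23 = 52.2% becomes 12/24 = 50.0%. For a rare event, such as one AESI, 1/23 = 4.3% becomes 1/24 = 4.2%. If every dosed child had a TEAE, the table would show at most 23/24 = 95.8% for k = 1.

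**Missing onset date**

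Suppose that the one undosed child has an undated event and the default in 4.3.5.1 is applied literally. The table then shows (12 + 1)/24 = 54.2%, against 12/23 = 52.2% on dosed patients. The error can therefore go upward as well.

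**Exposure and compliance**

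- Duration of exposure is last dose date minus first dose date, plus 28 or 14 days according to regimen. Neither date exists for an undosed child. The lowest exposure category is 1 day, and there is none for no exposure.
- Compliance counts planned administrations up to the last IMP date. Without such a date the ratio is 0/0.
- Section 3 leaves missing data out of percentages, so the likely result is a table with a smaller N than the population it is headed with, and not a shifted percentage.

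**The case against.** The strongest reply is that the wide definition has a sensible purpose. Tape stripping is a study procedure applied repeatedly to children, and a child who was stripped but not dosed should not disappear from the safety reporting. The SAP does not give this reason, but the criterion is the one it uses for healthy volunteers. This stands as a reason to keep 4.2.4. It does not justify the denominator of a treatment-emergent table, because events before dosing are by definition not treatment-emergent, and 4.3.5.1 already provides a separate summary for events outside that period.

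A second reply is that little would be hidden. All adverse events are listed, the TEAE tables give counts as well as percentages, and 4.3.1.3 reports the size of the safety and ITT populations with reasons for exclusion. Because ITT requires a dose, a reader could recompute the percentages. Healthy volunteers have no TEAE summary, so no comparison between cohorts is distorted. The sponsor's reporting standards cited in 4.3 and 4.3.5 may also set a denominator convention; they are not available here. All of this limits the importance, but the rule as written in the SAP is unchanged by it.

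Four stronger readings are tempting, and the document does not support them:

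- A reader might infer that adverse event incidence is understated. That holds only if at least one child is assessed and not dosed, and the SAP neither gives nor suggests such a number.
- A reader might infer that an undosed child can never be in the numerator. The default for missing onset dates could put one there.
- A reader might infer that exposure and compliance percentages are biased. They are undefined for that child, and missing values are left out of percentages.
- A reader might conclude that 4.2.4 should simply require a dose. Through 4.3.5 this would remove stripped but undosed children from every safety analysis.

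**Conclusion.** The plan is wrong as written on a small point. It admits AD patients to the safety population without a dose and bases TEAE, AESI, exposure and compliance tables on that population. Nothing in the SAP limits the TEAE denominator to dosed patients.

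The consequence is conditional. If k = 0, nothing changes. For k = 1 or 2, dilution alone multiplies TEAE and AESI percentages by 0.958 or 0.917, which is about 2 to 4 percentage points on a rate near 42%, and almost nothing on a single event. The figures assume 24 AD patients in the safety population, k of them undosed. No conclusion about skin barrier function depends on it. It is worth correcting because it is cheap and would otherwise be settled during programming.

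**What to change.** Leave 4.2.4 as it stands, and make these changes:

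1. In 4.3.5.1, state that the TEAE and AESI tables use AD patients of the safety population who had at least one dose of IMP.
2. In 4.3.2.4, state the same for exposure and compliance.
3. In 4.3.5.1, apply the default that treats an event with a missing or incomplete onset date as treatment-emergent only to dosed patients.
4. In 4.3.5.1, report events of assessed but undosed AD patients together with the events outside the treatment-emergent period.

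The cost is a few sentences in two sections and one additional denominator that must be footnoted in the tables. No data collection changes, and events caused by tape stripping are still reported.

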4.3 STATISTICAL METHODS

All analysis variables will be described according to the methods defined in [Section 3](#) for the description of continuous and categorical variables.

The reporting of the efficacy and safety statistical analyses will be programmed according to the recommendations and templates of the BTD-009094 “Summarizing and reporting standard Early Development clinical trial data (except oncology)” Version 4.0 dated 02-Feb-2021.

